3 STATISTICAL METHODOLOGY

3.1 General Considerations

3.1.1 Analysis Day

Analysis day will be calculated from the date of first dose of Remodulin. The day of the first dose of study drug will be Day 1, and the day immediately before Day 1 will be Day -1. There will be no Day 0.

3.1.2 Analysis Visits

Nominal visits will be used for analysis. Number of weeks after transition visit will also be derived using the nominal visit.

3.1.3 Definition of Baseline and transition visit value

Baseline is defined as the last measurement prior to the initiation of Remodulin.

Transition visit value is defined as the last measurement prior to the first dose of Orenitram.

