- ⁱ A full physical examination is an evaluation of general appearance; mental examination; head, ear, eyes, nose, and throat examinations; and examination of dermatologic, cardiovascular, respiratory, gastrointestinal, musculoskeletal, and neurologic body systems.
- ^j Vital signs include blood pressure, heart rate, respiration rate, height, and weight. Vital signs must be collected after 5 minutes of rest while seated. No other measurements or procedures should occur during the 5 minutes of rest. Vital signs will be collected prior to or at least 30 minutes after the 6MWT.
- Urine pregnancy tests will be conducted on all female subjects of childbearing potential. A negative urine pregnancy test is required of all female subjects of childbearing potential to be eligible for the study and remain enrolled as a subject.
- Blood samples for NT-proBNP must be drawn prior to conducting the 6MWT and will occur at the Screening Visit, Baseline Visit (prior to Remodulin initiation), the Transition Visit (prior to Orenitram initiation), and the Week 16/Early Study Withdrawal visit.
- Where local regulations allow, the subject's blood sample will be collected for pharmacogenomic (genetic/RNA) and biomarker analysis for those subjects who consent to the optional testing.
- The subject should rest (seated) for 10 minutes before each 6MWT. If the 6MWT is conducted using supplemental oxygen at Baseline, then all subsequent 6MWTs during the study should be conducted with supplemental oxygen. Similarly, if the Baseline assessment is conducted without supplemental oxygen, then subsequent assessments should also be conducted without oxygen. All efforts should be made to keep the supplemental oxygen flow rate consistent during the 6MWT. The supplemental oxygen flow rate must be recorded at every 6MWT, if applicable. The Borg dyspnea score and heart rate recovery (1 minute) should take place immediately following the 6MWT.
- At the Transition Visit, 6MWT should occur with the subject still on Remodulin therapy, before initiating the transition to Orenitram.
- P When the subject is receiving Orenitram, the 6MWT should occur within 2 to 6 hours of the subject's most recent dose.
- ^q Study drug refers to both Remodulin and Orenitram.

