Transition may be reversed or stopped if the Investigator feels it is necessary due to significant signs or symptoms of PAH or due to serious safety concerns. If the Investigator deems a subject unsuitable for transition to Orenitram due to significant signs or symptoms of PAH or any other serious safety concerns, the subject may remain on Remodulin for the duration of the study. However, the subject should be continually assessed to determine if they become stable enough for transition to Orenitram. All subjects still on Remodulin at Week 8 should transition to Orenitram regardless of their Remodulin dose unless the Investigator deems them unsuitable for transition to Orenitram due to significant signs and symptoms of PAH or any other serious safety concerns.

Following completion of transition, Orenitram dose titration will continue in the outpatient setting through Week 16 to reach the maximum tolerated dose by increasing the dose by 0.125 mg TID every 3 to 4 days as tolerated, with the goal of achieving a maximum tolerated dose by the end of Week 16. A slower titration rate may be used if the subject experiences adverse effects. There is no maximum Orenitram dose during the study.

Orenitram will be dosed TID with food. Dosing will take place approximately every 6 to 8 hours, with adjustments permitted based on the subject's lifestyle and schedule. Study subjects should take their study drug at approximately the same times each day. Tablets must be swallowed whole and not chewed, as this will result in inappropriate delivery of the active ingredient. If the tablet is inadvertently damaged during administration, the subject/caregiver should contact site personnel to be monitored for the onset of symptoms due to possible inappropriate drug release. Subjects must not "make-up" or "double-up" on missed doses of

Orenitram. If dosing is interrupted for longer than 24 hours, consideration should be given to gradually re-titrating the subject's dose to the last dose administered prior to the dose interruption, particularly in cases where the last dose prior to interruption was greater than 3 mg.

In the event of a planned short-term treatment interruption for subjects unable to take oral medications after beginning transition to Orenitram, consider a temporary infusion of SC or IV Remodulin using the following equation to calculate the dose of Remodulin:

Remodulin (ng/kg/min) =
$$(139 \times \text{Orenitram TDD [mg]}) \div \text{weight (kg)}$$

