7 EXPERIMENTAL PROCEDURES

The following study visits will occur during the 16-week study at the following time points: Screening, Baseline, Week 2 (Day 15 [±3 days]), Week 4 (Day 29 [±5 days]), Week 8 (Day 57 [±5 days]), Post Transition Visit (7 to 14 days after Transition Visit), Week 12 (Day 85 [±5 days]), and Week 16/Early Study Withdrawal (Day 113 [±7 days]). The Transition Visit should occur at Weeks 2, 4, or 8.

Written informed consent must be obtained from all subjects (signed and dated by subject) prior to study procedures. The patient-reported outcomes (ie, TSQM and the emPHasis-10 questionnaire) should be completed by the subjects prior to other assessments listed in Table 3-1. Subject information from assessments listed in Table 3-1, including the

patient-reported outcomes, will be collected and recorded into an EDC system by study site personnel or the Investigator.

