7.3.1 Week 2 (Day 15 [±3 Days])

Subjects will continue study drug dosing in the outpatient setting, as clinically appropriate. Subjects will return to the study site clinic for the following Investigator-reported assessments:

- Record of AEs
- WHO FC
- 6MWT (after 10 minutes rest [seated]), immediately followed by heart rate recovery (1 minute) and Borg dyspnea score. If the subject is receiving Orenitram, the 6MWT should occur within 2 to 6 hours of the most recent dose.
- Concomitant medications

- Vital signs (prior to or at least 30 minutes after the 6MWT, and after 5 minutes rest seated)
- Drug accountability (see Section 11.5)
- If the Transition Visit occurs at Week 2, please perform additional assessments listed in Section 7.3.4.

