3.4.2 Secondary Efficacy Endpoints

Secondary efficacy endpoints will be summarized by visit, as applicable. The change from Baseline at each visit will be summarized for each parameter. For study visits occurring after the Transition Visit, the change from Transition Visit will also be summarized for each parameter in addition to the change from Baseline. The continuous secondary endpoints will also be summarized on Transition Visit and X Weeks Post Transition Visit in addition to the nominal visits. The value of interest listed in section 2.3.2.2 will be provided.

- 6-Minute Walk Distance (6MWD)
 - The subjects receiving oxygen during the time of the test will be listed
 - The subjects having unusual circumstances that adversely affected the walk will be listed
- Heart rate recovery after 6MWD
- Borg dyspnea score
 - The Borg dyspnea scores and their respective shifts from baseline and Transition Visit will be summarized for each assessment (i.e. number and percent of subjects who improved, worsened, or had no change)
- World Health Organization (WHO) Functional Classification (FC)
 - The functional class values and their respective shifts from baseline and Transition Visit will be summarized for each assessment (i.e. number and percent of subjects who improved, worsened, or had no change)
- N-terminal pro-brain natriuretic peptide (NT-proBNP)
 - o The percent change from Baseline and Transition Visit will also be provided.
- · Echocardiographic parameters
- PAH symptom score
 - Severity grade values (i.e., 0, 1, 2, or 3) for each symptom of PAH (fatigue, dyspnea, edema, dizziness, syncope, chest pain, and orthopnea) will be listed for all subjects. The severity grades and their shifts from baseline and Transition Visit will be summarized for each assessment.
- Subjects' TSQM responses and Health-related quality of life (emPHasis-10) questionnaires

- The number and percentage of subjects that successfully transitioned to Orenitram at any dose and were successfully maintained on therapy at Week 16
- The number and percentage of subjects that improve in each of the following 4 individual clinical parameters (6MWD, NT-proBNP, WHO FC, right atrial area) to a lower risk stratum, as defined by the 2015 European Society of Cardiology guidelines, compared to Baseline will be provided for the Transition Visit and Week 16.

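### SAP 3.1.3 does not require the Transition value to be measured on Remodulin, so for six assessments a missed or unscheduled Transition test can be replaced by the pre-Remodulin Baseline

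*SAP*

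**What the plan says.** SAP 3.1.3 gives two definitions. The first is "Baseline is defined as the last measurement prior to the initiation of Remodulin". The second is "Transition visit value is defined as the last measurement prior to the first dose of Orenitram". The second has an upper limit in time (first Orenitram dose) but no lower limit. SAP 3.1.2 adds "Nominal visits will be used for analysis" and does not say how that combines with 3.1.3.

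The Transition value is used twice. It is the end point of the change from Baseline (SAP 2.3.2.2), and it is the reference for later visits, where "the change from Transition Visit will also be summarized for each parameter in addition to the change from Baseline" (SAP 3.4.2). It also feeds the Transition Visit risk-stratum and low-risk percentages (SAP 3.4.2) and the change from Transition on the AE Bothersome Survey (SAP 3.7.1.1).

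On timing, Protocol 7 says "The Transition Visit should occur at Weeks 2, 4, or 8". Protocol 6.1 and 7.3.4 nevertheless let a subject judged unsuitable stay on Remodulin, and say that "the subject should be continually assessed to determine if they become stable enough for transition to Orenitram". Transition after Week 8 is therefore possible.

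On the schedule, a footnote to Protocol Table 3-1 places NT-proBNP at Screening and then at "Baseline Visit (prior to Remodulin initiation), the Transition Visit (prior to Orenitram initiation), and the Week 16/Early Study Withdrawal visit". The table shows echocardiography, TSQM, emPHasis-10, PAH symptom score and the AE Bothersome Survey at Baseline, Transition and Week 16. Protocol 7.3.3 adds the Transition tests at Week 8 only if transition happens then, and Protocol 7.3.6 (Week 12) lists none of them. The walk test is different. From Week 2 on, each visit includes "6MWT (after 10 minutes rest [seated]), immediately followed by heart rate recovery (1 minute) and Borg dyspnea score" whether or not the subject transitions, and WHO FC follows the same pattern.

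**The concern.** The Transition value is meant to show where the subject stands at the end of Remodulin induction. A Baseline measurement also satisfies the definition, because it too was taken before the first Orenitram dose. For the six assessments scheduled only at Baseline and Transition, it is the next one back if the Transition test is not there.

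For such a subject the induction change is reported as zero, and whatever happened on Remodulin is counted in the Transition-to-Week 16 change, the Orenitram part of the study. The Transition Visit risk percentages for NT-proBNP and right atrial area would describe the subject before any study drug. The AE Bothersome Survey has a further difficulty. Subjects with recent prostacyclin-class therapy are excluded (Protocol 4.2), so a carried-forward Baseline survey would omit side effects on Remodulin and could make them appear to arise on Orenitram. That bears on the tolerability hypothesis in Protocol 1.4.

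The substitution would also be hard to see. The value counts as non-missing, and the SAP declares carrying forward only for Week 16. The affected subjects need not be typical either: the stated reasons for staying on Remodulin past Week 8 are significant signs or symptoms of PAH, or serious safety concerns.

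**Working it through.** The plan gives no figure that depends on this rule, so there is nothing to reproduce. The check has two steps.

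**Step 1. Apply SAP 3.1.3 to the schedule.** Inputs: visit days 15, 29, 57 and 85 for Weeks 2, 4, 8 and 12 (Protocol 3.1), and the assessments per visit (Protocol Table 3-1 and 7.3.1 to 7.3.6). Assume that the Transition test was not done and that the other scheduled visits were attended. The value selected is:

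| Assessment | Missed at Week 2 transition | Missed at Week 4 | Missed at Week 8 | Starts between Weeks 8 and 12, no test at start | Starts after Week 12, no test at start |
|---|---|---|---|---|---|
| NT-proBNP, ECHO, TSQM, emPHasis-10, PAH symptom score, AE Bothersome Survey | Baseline | Baseline | Baseline | Baseline | Baseline |
| 6MWD, Borg, WHO FC | Baseline | Day 15 | Day 29 | Day 57 | Day 85 |

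In the first row the rule returns a pre-Remodulin value every time. In the second row it does so only in the first column; elsewhere it returns an on-Remodulin value.

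**Step 2. Size.** Let n subjects contribute, with k of them carrying Baseline forward. Let d_u be the true mean Baseline-to-Transition change in the other n − k, and d_a the true mean in the k affected.

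- True mean change: (1 − k/n)·d_u + (k/n)·d_a
- Reported mean change: (1 − k/n)·d_u, because the k contribute zero
- Shortfall: (k/n)·d_a

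For those with a Week 16 value, the same quantity is added to the mean Transition-to-Week 16 change. The total from Baseline to Week 16 does not move. These identities hold for means of absolute or log change, not for medians or mean percent change.

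If the affected subjects are otherwise average (d_a = d_u), the reported mean is the true mean times (1 − k/n). The documents do not give k, so k = 1 to 7 is an assumption.

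- n = 35 (SAP 2.2.3): 1 − 1/35 = 0.971; 1 − 7/35 = 0.800
- n = 30 (Protocol 10.2): 1 − 1/30 = 0.967; 1 − 7/30 = 0.767

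As an illustration on the log scale with n = 35, an assumed true NT-proBNP ratio to Baseline of 0.70 would be reported as 0.70^(34/35) = 0.707 with one subject affected, and 0.70^(28/35) = 0.752 with seven.

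**The case against.** Three arguments on the other side carry weight.

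First, SAP 3.1.2 uses nominal visits, and summaries count non-missing values (SAP 3.1.5). On that reading a Transition echocardiogram that was not done is simply missing, and LOCF is stated for Week 16 only. This is a possible reading. But 3.1.3 is the specific definition of this value, and nothing says which section prevails. Two programmers could produce different tables, which supports clarifying the text.

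Second, a site may well run the Transition tests on the day a late transition starts. Protocol 7.3.4 attaches them to the Transition Visit, and nothing bars that visit after Week 8. SAP 3.1.3 would pick such a value up correctly. This stands: late transition alone does not produce the error. It also needs the absence of any test before Orenitram, and the protocol schedules none at that point.

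Third, the consequences are limited. The primary endpoint is the Week 16 Orenitram dose and does not use the Transition value. No formal testing is done (SAP 3.1.6). With one subject affected the shift is about 3%.

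A reader might infer that every late transitioner has Baseline reported as the Transition value on every endpoint. The schedule does not support that, because 6MWD, Borg and WHO FC have on-Remodulin values at Weeks 2, 4, 8 and 12. So two of the four risk parameters, 6MWD and WHO FC, are largely unaffected. A reader might also want to quote a spurious percentage fall in NT-proBNP credited to Orenitram. The documents do not support a figure: the number affected and the induction effect are unknown, and the optional log-scale model in SAP 3.4.2 covers changes from Baseline, not a Transition-to-Week 16 ratio.

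**Conclusion.** The point holds in a limited form. Read literally, SAP 3.1.3 allows a pre-Remodulin measurement to stand as the Transition value for NT-proBNP, ECHO parameters, TSQM, emPHasis-10, PAH symptom score and the AE Bothersome Survey. It happens when the Transition test is missed, or when transition starts after Week 8 with no test before Orenitram. For each such subject the induction change is set to zero and moved into the Transition-to-Week 16 change, and the Transition percentages for NT-proBNP and right atrial area are distorted. 6MWD, Borg and WHO FC share the problem only for a test missed at a Week 2 transition.

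The overall size depends on an unknown count. Under the average-subject assumption the mean Baseline-to-Transition change keeps 97% to 80% of its value for 1 to 7 affected of 35, or 97% to 77% of 30. If the affected subjects respond differently from the rest, the shortfall is (k/n)·d_a and could be smaller or larger. The text should be corrected because the remedy is a sentence or two, but this does not threaten the main result.

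**What to change.** In SAP 3.1.3, define the Transition value as the last measurement taken after the first dose of Remodulin and before the first dose of Orenitram, and set it to missing if there is none. State that this definition takes precedence over the nominal-visit rule in 3.1.2 for the Transition value.

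In Protocol 7.3.4 and Table 3-1, state that the Transition assessments already planned are done before the first Orenitram dose whenever transition starts. This reconciles the Week 2, 4 or 8 timing of the visit with the passages that allow later transition. It concerns the timing of assessments only and changes no dosing or suitability rule.

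As optional extras, the tables could show how many Transition values are missing or were taken before the Transition Visit, and SAP 3.3.7 could add a group for transition after Week 8. Doses are already listed by subject and visit, so the second is a convenience.

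The cost is a sentence or two in each document. A few Transition values become missing, and the contributing n falls by that number. Those gaps may not be random, but they would be visible. A few late transitioners would have the planned tests on a different day.

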3.1.4 Definition of Treatment Phases

"Remodulin phase" is defined as the portion of the study when a patient is receiving Remodulin only.

"Transition phase" is defined as the portion of the study beginning at the Transition Visit when a patient is receiving both Remodulin and Orenitram. "Transition phase" ends at the last dose of Remodulin if the transition is "successful". "Transition phase" ends at the last dose of Orenitram if the transition is "unsuccessful" and reversed. "Transition phase" ends at the last dose of Orenitram and Remodulin if the transition is stopped.

"Orenitram phase" is defined as the portion of the study when a patient is receiving Orenitram only.

3.1.5 Summary Statistics

The efficacy and safety data in the study will be presented in summary tables and listings in the final clinical study report. Listings will be sorted by subject, visit, and time point assessment (if applicable). For summary tables, the data will be summarized by visits (including the Transition Visit) and time point assessment, if appropriate. For continuous variables in general, descriptive statistics will include the number of observations (non-missing values), mean, standard deviation (SD), median, inter-quartile range, minimum, and maximum. Change from Baseline will also be provided if applicable. For categorical variables, descriptive statistics will include the frequency and percentage in every category.

3.1.6 Hypothesis Testing

No formal statistical testing will be performed.

3.1.7 Multiple comparisons and multiplicity

No adjustments for multiplicity will be made in these analyses.

3.2 Analysis Populations

3.2.1 Safety Population

The Safety Population is defined as all subjects in the study who received study drug (Remodulin or Orenitram). All safety analyses will be performed on the Safety Population.

3.2.2 Per-protocol Population

The Per-protocol Population is defined as all subjects in the study who received study drug without any major deviations (which may interfere with efficacy evaluation).

3.2.3 Completer Population

The Completer Population is defined as all subjects in the study who complete the study without any major deviations (which may interfere with efficacy evaluation) and are receiving Orenitram at Week 16.

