2.3 Study Endpoints

2.3.1 Primary Endpoint

The primary efficacy endpoint is the percentage of subjects achieving an Orenitram dose of 4 mg TID (or a total daily dose of 12 mg) or higher at Week 16 (or a dose of 0.057 mg/kg TID [or a total daily dose of 0.171 mg/kg] or greater for subjects <70 kg).

The prescribed total daily dose will be used for the primary efficacy endpoint.

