3.3.7 Study Drug Exposure

A listing of Orenitram and Remodulin dose levels for each subject at each timepoint will be provided by visit.

A summary of Orenitram and Remodulin dose levels at each study visit will be provided for the Safety Population. Summary of dose levels at each study visit will also be provided for patients who transition at week 2, week 4, and week 8 separately. Change from baseline Remodulin dose levels will also be provided.

Days of exposure to study drug (Remodulin and Orenitram) will be calculated as date of last dose of study drug – date of first dose of study drug + 1. Note that the exposure calculation is intended to describe the length of time a subject was exposed to study drug and therefore does not take study drug interruptions into account. Days of exposure to study drug will be

summarized based on the Safety Population with descriptive statistics and with counts and percentages of subjects with exposure in the following categories:

- <4 weeks (<28 days)
- 4 -<8 weeks (28 55 days)
- 8 <12 weeks (56 83 days)
- 12 <16 weeks (84 111 days)
- ≥16 weeks (≥112 days).

Days of exposure to Remodulin and Days of exposure to Orenitram will also be summarized in the same way.

Number and percentage of subjects who initiated Remodulin in an inpatient vs. outpatient setting will be summarized.

Number and percentage of subjects who initiated Remodulin via IV or SC routes will be summarized

Number and percentage of subjects who switched between IV and SC routes for Remodulin will be summarized

For patients initiating Remodulin in the inpatient setting, the Remodulin dose at discharge will be summarized.

Number and percentage of subjects who initiated transition from Remodulin to Orenitram in an inpatient vs. outpatient setting will be summarized.

Summary statistics will be provided for:

- Time to Transition to Orenitram, calculated as date of first dose of Orenitram date of first dose of Remodulin + 1
- Duration of inpatient stay (for applicable subjects) for Remodulin initiation
- Duration of transition (days receiving both Remodulin and Orenitram)
- Duration of inpatient stay (for applicable subjects) for transition to Orenitram
- Dose of Remodulin (ng/kg/min) at Transition Visit
- Prescribed total daily dose of Orenitram (mg) at the Post-Transition visit

All the above summaries will be based on the Safety Population.

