3.4.1 Primary Efficacy Endpoint

The number and percentage of subjects achieving an Orenitram dose of 4 mg 3 times daily (TID) (or a total daily dose of 12 mg) or higher (or a dose of 0.057 mg/kg TID [or a total daily dose of 0.171 mg/kg] or greater for subjects <70 kg) will be summarized for Week 16 for the Per-Protocol population. Subjects with missing data for prescribed total daily dose at Week 16 will be considered as not achieving the primary efficacy endpoint.

This will be repeated for the Completer Population.

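### A Remodulin infusion after the cross-taper stretches the SAP's Transition phase and Remodulin exposure over Orenitram-only weeks; separately, a subject on both drugs at Week 16 can count as a success

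*SAP*

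**What the plan says.** **Phases (SAP 3.1.4).** The Remodulin and Orenitram phases are time on that drug alone. The Transition phase starts at the Transition Visit, is described as time on both drugs, and "ends at the last dose of Remodulin if the transition is" successful. If the transition is unsuccessful and reversed, it ends at the last Orenitram dose. If it is stopped, it ends at the last dose of both. SAP 3.7.1 reports prostanoid adverse events and their maximum severity separately by phase.

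**Exposure (SAP 3.3.7).** Exposure to study drug is last dose minus first dose plus 1, and the SAP says openly that interruptions are ignored. It then adds: "Days of exposure to Remodulin and Days of exposure to Orenitram will also be summarized in the same way".

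**Later Remodulin (Protocol 6.1).** In a planned short interruption of oral dosing after transition has begun, sites may "consider a temporary infusion of SC or IV Remodulin". For a subject judged unsuitable for transition and kept on Remodulin, "the subject should be continually assessed to determine if they become stable enough for transition to Orenitram", with no stated last date. A transition may also be stopped or reversed.

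**Primary endpoint and populations.** SAP 3.4.1 summarises "The number and percentage of subjects achieving an Orenitram dose of 4 mg 3 times daily (TID") or higher, with a weight-based threshold below 70 kg. SAP 2.3.1 adds: "The prescribed total daily dose will be used for the primary efficacy endpoint". The Per-protocol Population is "all subjects in the study who received study drug without any major deviations" that may interfere with efficacy evaluation. The Completer Population comprises subjects who "complete the study without any major deviations (which may interfere with efficacy evaluation) and are receiving Orenitram at Week 16".

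**The concern.** The phase and exposure rules work for a subject who goes once from Remodulin, through a cross-taper, to Orenitram. They do not work when Remodulin is given again after the taper. The last Remodulin dose is then the end of the later infusion, not of the taper, and everything in between is swept into the Transition phase and into Remodulin exposure. SAP 3.1.4 also defines that interval as the Orenitram phase, so one day can belong to two phases. The output at stake is the prostanoid adverse event table by phase, which is how the study describes tolerability before, during and after transition, together with the per-drug exposure tables.

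The second, smaller matter is that the primary objective concerns the Orenitram dose reached after induction. A subject who meets the dose threshold at Week 16 while still receiving Remodulin has not shown that the oral dose stands alone. The written rules nevertheless count that subject as a success and, if a Completer, place the subject in the subgroup of Completers meeting the primary endpoint that SAP 3.4.2 uses for secondary endpoints.

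**Working it through.** The plan states no figure for these quantities, so the check applies its rules to courses that the protocol allows. The dates in steps 1 to 4 are assumed.

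**1. Temporary infusion after the taper.** Remodulin is given on Days 1 to 36, Orenitram from Day 29, and temporary Remodulin without oral drug on Days 80 to 81.

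| Quantity | SAP rule | Actual days |
|---|---|---|
| Remodulin exposure | 81 − 1 + 1 = 81 | 36 + 2 = 38 |
| Transition phase | 81 − 29 + 1 = 53 | 36 − 29 + 1 = 8 on both drugs |
| Time to transition | 29 − 1 + 1 = 29 | 29 |
| Duration of transition (days on both drugs) | 8 | 8 |

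The exposure excess is 81 − 38 = 43 days, which is Days 37 to 79, all Orenitram-only. The phase excess is 53 − 8 = 45 days: those 43 plus the 2 infusion days. The subject also changes category in the SAP 3.3.7 exposure table, from 28–55 days (38) to 56–83 days (81).

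**2. Adverse events by phase.** A headache on Day 60 of this example occurs on Orenitram alone. Under the end rule it falls in the Transition phase; by the definition of the Orenitram phase it falls there too. If the description of the Transition phase as time on both drugs is taken to govern instead, Day 60 is correctly placed, but Days 80 to 81 become Remodulin-only and mix with induction. The split by phase is affected either way.

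**3. Return to Remodulin after completed transition.** Take the same start, but Remodulin alone on Days 80 to 113. Remodulin exposure is 113 − 1 + 1 = 113 days against 36 + (113 − 80 + 1) = 70 actual. If the transition is classed as successful, the Transition phase is 113 − 29 + 1 = 85 days. If it is classed as reversed, the phase ends at the last Orenitram dose: 79 − 29 + 1 = 51 days. Neither matches the 8 days on both drugs.

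**4. Range.** With transition starting on Day 29, tapers of 9, 17 or 21 days, and temporary infusions on Days 60–62, 90–94 or 100–106:
- Remodulin exposure is overstated by between 62 − (49 + 3) = 10 days (21-day taper, Days 60–62) and 106 − (37 + 7) = 62 days (9-day taper, Days 100–106).
- The Transition phase is overstated by between 34 − 21 = 13 days and 78 − 9 = 69 days in the same two cases.

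**5. Both drugs at Week 16.** The latest scheduled Week 8 transition starts on Day 57 + 5 = 62. A 21-day taper ends by about Day 62 + 21 = 83, and the earliest Week 16 visit is Day 113 − 7 = 106. Nobody on the normal schedule is still tapering. For a Day 113 visit, overlap through a taper needs a late start, between Day 113 − 20 = 93 and Day 113; otherwise it needs a stopped transition that leaves the subject on both drugs.

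Could such a subject meet the threshold? In the 17-day examples of Protocol Appendix I it is met with Remodulin still above 0 in 7 of 9 (4 mg TID at 70 and 120 kg; 0.057 × 40 = 2.28 mg TID at 40 kg). At 120 kg starting from 40 ng/kg/min, 4.375 mg TID is reached with Remodulin at 25 ng/kg/min, which is 25/40 = 62.5% of the start. This shows that it is possible, not how often it happens.

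Each such subject moves the primary percentage by 1/35 = 2.9 points (SAP sample size) or 1/30 = 3.3 points (protocol sample size).

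**The case against.** There is a good deal to say for the plan, and most of it stands.

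- **Length of induction.** A reader might infer that the SAP misreports how long induction and transition lasted. It does not. SAP 3.3.7 separately summarises time to transition and days on both drugs; in the example these are 29 and 8, both correct.
- **Reversal.** A reader might infer that every reversed subject is mishandled. SAP 3.1.4 has its own end rule for reversal, which works during the taper, and a subject fully back on Remodulin has no qualifying Orenitram dose. What remains is a return after completed transition, or a reversed and repeated one.
- **Temporary infusion at the Week 16 visit.** A reader might infer that this subject passes as a success unnoticed. Such a subject cannot take oral drug, so is arguably not receiving Orenitram. The actual-dose analysis in SAP 3.4.1.1 also scores missed doses as 0 mg. It does not, however, catch a subject taking both drugs.
- **The 7-of-9 figure.** It describes doses during a taper and is not a rate of error at Week 16. Protocol 7 says the Transition Visit should fall at Weeks 2, 4 or 8, so late transition is inferred from continued assessment rather than scheduled.
- **First-to-last exposure.** This is a disclosed convention and suits study drug overall. The difficulty arises only when it is carried over to each drug, because the gap in one drug is then time on the other.

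The visit listings of both doses and the disposition count of returns to Remodulin make these cases visible. They do not alter the phase, exposure or primary endpoint rules. That the study is descriptive, with no formal testing, limits the consequence but does not make a wrong tabulation right.

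**Conclusion.** The point holds for phases and per-drug exposure. For a subject given Remodulin again after the cross-taper, the written rules produce overlapping phases, misplace prostanoid adverse events and count Orenitram-only weeks as Remodulin exposure. In the assumed example the overstatement is 43 days of Remodulin exposure and 45 days of Transition phase; over the dates tried for a temporary infusion it is 10 to 62 and 13 to 69 days. The sizes rest on assumed dates, and the documents do not say how many subjects will follow such a course.

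The Week 16 part holds only as an undefined edge case. The rules let a subject on both drugs count as a success, but this needs a late or stopped transition, so few if any are likely, at 2.9 points each with 35 subjects. The documents do not support reading the primary result as materially inflated. Nor do they support redefining success: Protocol 10.3.1.1 defines it by Orenitram dose alone, and a sensitivity analysis is the proportionate answer.

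**What to change.** - **SAP 3.1.4:** end the Transition phase of a completed transition at the last Remodulin dose of the cross-taper. Label any later Remodulin, whether temporary or a return, as a separate interval, and say how SAP 3.7.1 tabulates adverse events in it.
- **SAP 3.3.7:** report exposure to each drug as the sum of days on that drug, where start and stop dates are available. Keep last minus first plus 1 for study drug overall.
- **SAP 3.4.1, with a cross-reference in 3.2.3:** keep the protocol's primary definition. Report the number of subjects receiving both drugs at Week 16, and add a sensitivity analysis, in both populations, that counts them as not achieving the endpoint.

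The cost is SAP wording and minor programming. Protocol 3.3.1.1 already has both doses recorded at every visit on study drug, which is enough for the Week 16 count. The sum of days also needs dates between visits, and the documents do not show that these are captured for temporary infusions; this should be confirmed before the rule is adopted. The sensitivity percentage may be slightly lower than the primary one. No clinical rule changes.
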